## 6. Image Interpretation

- Describe the location of the primary tumor and of metastatic lesions if present.
- Measure and record the maximum SUV in the primary tumor and most active metastatic lesion.
- If the diameter of the primary tumor is less than 2 cm or the primary tumor demonstrates only low FDG uptake, measure the maximum SUV of the lesion with the highest FDG uptake.
- Measure and record the mean SUV in the liver as described in [Section 5](#) above.

## APPENDIX C

### CT Acquisition Parameters and Image Data Analysis

Additional Information for the CT Acquisition Parameters and Volumetric Analyses are also available on the ACRIN web site at ([www.acrin.org/6678\\_protocol.aspx](http://www.acrin.org/6678_protocol.aspx)).

#### Acquisition and Analysis of the CT Scans

The CT scans serve three purposes: (a) attenuation correction and registration with PET scans for anatomic localization of FDG uptake; (b) response assessment using RECIST; and (c) high spatial quality data sets for central volumetric analyses of lung lesions. Depending upon considerations of workflow and the need for intravenous contrast, individual institutions may have different processes for completing the chest CT scans used for RECIST and tumor volumetric assessments. The following are potential scenarios:

- **Single Platform:** fusion PET/CT scanner: All studies are performed on a fusion PET/CT scan, including the PET/CT scanner, and one single inspiratory CT without contrast for both RECIST criteria and tumor volumetry.
- **Single Platform:** fusion PET/CT scanner: All studies are performed on a fusion PET/CT scan, including the PET/CT scanner, an inspiratory CT with contrast for RECIST criteria, and an inspiratory CT without contrast for tumor volumetry.
- **Dual Platforms:** Fusion PET/CT scanner used to perform a PET/CT scan and an inspiratory CT without contrast for tumor volumetry as well as a dedicated, standalone CT scanner to perform a CT with contrast for RECIST criteria.

#### 1. CT Volumetry

##### 1.1 Image Acquisition

To ensure the level of spatial quality necessary for tumor volumetric analyses, the scanner platforms must be able to perform prospective reconstructions of a single helical sequence at different slice thicknesses. The following are representative PET/CT systems:

- Siemens Biograph PET/CT (CT scanners 6,16, 64-slice); Siemens Medical Solutions | Malvern, PA.
- GE Discovery PET/CT scanners; GE Healthcare Technologies | Waukesha, WI, USA
- Philips Gemini PET/CT scanners (Brilliance CT: 6, 10, 16, 40-slice; 40 and 64 channel); Philips Medical Systems | Andover, MA, USA

All CT scans for an individual participant should be performed on the same platform throughout the trial. In the rare instance of equipment malfunction, follow-up scans on an individual participant can be performed on the *same type* of platform.

Each scanner platform has slightly different technical specifications and user inputs for imaging parameters. The following table provides specifications for the acquisition and reconstruction parameters for the CT series performed for tumor volumetry.

**Table 1. Parameters for the CT scans used to measure tumor volume.**

| Parameter  | Diagnostic CT Scan
for Tumor Volumetry |
|---|---|
| KV   | 120   |
| Gantry rotation time                                   | ≤ 0.5 sec   |
| Scanner Effective mAs
(Regular-large size patient) | 100-260   |
| Maximum scan   breath-hold time (40 cm long thorax)    | ≤ 15 sec  |
| Number of active channels (N)                          | ≥ 6   |
| Maximum Reconstructed slice width                      | 1-1.5 mm  |
| Reconstruction interval                                | 0 – 20% overlap                                   |
| Reconstruction algorithm                               | Standard  |
| Reconstruction diameter (dFOV)                         | outer rib to outer rib                            |
| Intravenous contrast media                             | None  |
| Arm positioning  | Above the head                                    |

Parameters for tumor volumetry should provide an in-plane voxel size of 0.55-0.75 mm.

## **2. Tumor Response Evaluation According To RECIST**

### **2.1 Image Acquisition**

Response assessment using RECIST criteria will be performed on all CT scans during the trial. Scans will be performed after administration of oral and IV contrast agents according to institutional practices.

Iodinated intravenous (IV) contrast media may be administered for diagnostic CT scans per standard institutional practice, unless contraindicated. The decision not to use IV contrast for CT is at the discretion of the performing radiologist. If IV contrast is *not* administered for these scans, then these non-contrast CT series can be used for both RECIST and volumetric measurements by prospectively reconstructing the image data into both thick (2.5 to 5 mm) and thin-section (1 to 1.25 mm) series, respectively..

The CT scan with contrast is obtained with arms elevated above the head and at suspended maximal inspiration to provide optimal relative contrast of lung lesions within aerated lung. Typical parameters for image acquisition and reconstruction are shown in Table 2.

**Table 2: Parameters for the CT scans used to assess tumor response according to RECIST**

| Parameter   | Dedicated CT for RECIST                            |
|---|--|
| KV  | 120  |
| Gantry rotation time                                | $\leq 0.5$ sec                                     |
| Scanner Effective mAs (Regular-large size patient)  | 100-260  |
| Maximum scan   breath-hold time (40 cm long thorax) | $\leq 15$ sec                                      |
| Number of active channels (N)                       | $\geq 6$   |
| Maximum Reconstructed slice width                   | 3 mm                                   |
| Reconstruction interval                             | 0-20% overlap                                      |
| Reconstruction algorithm                            | Standard   |
| Reconstruction diameter (dFOV)                      | outer rib to outer rib                             |
| Intravenous contrast media                          | Per institution practice   indication  |
| Arm positioning                                     | Above the head                                     |

1 If the inspiratory scan of the PET/CT is non-contrast, it *also* should be used for tumor volumetry, and prospectively reconstructed at 1-1.25 (volumetry) and 2.5-5 mm (diagnostic interpretation using RECIST) slice thicknesses.

2. Intravenous contrast should be administered according to standard practices with respect to amount, flow rates, and timing with respect to image acquisition, depending upon the body parts imaged. The same method of contrast administration should be followed with all subsequent scans.

## 2.2 Image Data Analysis

**2.2.1** The following categories of disease will be used in determining response to treatment by RECIST:

- **Measurable disease:** The presence of at least one measurable lesion. If the measurable disease is restricted to a solitary lesion, its neoplastic nature should be confirmed by cytology | histology.
- **Measurable lesions:** Lesions that can be accurately measured in at least one dimension with longest diameter  $\geq 10$  mm with helical CT.
- **Non-measurable lesions:** all other lesions, including small lesions (longest diameter  $< 20$  mm with conventional techniques or  $< 10$  mm with helical CT scan), i.e., bone lesions, leptomeningeal disease, Ascites, pleural/pericardial effusion, inflammatory breast disease, lymphangitic cutis | pulmonis, cystic lesions, and also abdominal masses that are not confirmed and followed by imaging techniques.

All measurements will be taken and recorded in metric notation on a calibrated diagnostic imaging workstation at full resolution using electronic calipers. The baseline measurements will be performed within one week of the start of treatment; measurements obtained following chemotherapy cycles will be obtained on scans performed within 1-3 days of the next cycle of treatment. The same method of assessment and the same technique will be used to characterize each identified and reported lesion at baseline and during follow-up. Lung lesions will be

evaluated on lung windows; mediastinal and or soft tissue lesions will be evaluated on soft tissue windows. The acquisition parameters provided above serve as guidelines for CT technique.

“Target” and “Non-Target” lesions will be documented according to the following guidelines:

- All measurable lesions up to a maximum of five lesions per organ and 10 lesions total, representative of all involved organs, should be identified as **target lesions** and recorded and measured at baseline.
- Target lesions should be selected on the basis of their size (lesions with the longest diameter and their suitability for accurate repeated measurements.
- A sum of the longest diameter (LD) for all target lesions will be calculated and reported as the baseline sum LD. The baseline sum LD will be used as reference by which to characterize the objective tumor response.
- All other lesions (or sites of disease) should be identified as non-target lesions and should also be recorded at baseline. Measurements of these lesions are not required, but the presence or absence of each should be noted throughout follow-up.

The following summarizes the categories of response:

| Response Criteria   | Evaluation of Target Lesions  |
|--|--|
| Complete Response (CR)   | Disappearance of all target lesions.   |
| Partial Response (PR)  | At least a 30% decrease in the sum of the LD of target lesions, taking as reference the baseline sum LD.   |
| Progressive Disease (PD)   | At least a 20% increase in the sum of the LD of target lesions, taking as reference the smallest sum LD recorded since the treatment started or the appearance of one or more new lesions. |
| Stable Disease (SD)  | Neither sufficient shrinkage to qualify for PR nor sufficient increase to qualify for PD, taking as reference the smallest sum LD since treatment start                                    |
|  | Evaluation of Non-Target Lesions  |
| Complete Response (CR)   | Disappearance of all non-target lesions and normalization of tumor marker level.   |
| Incomplete Response;
Stable Disease (SD)  | Persistence of one or more non-target lesions(s) or/and maintenance of tumor marker level above the normal limits  |
| Progressive disease  | Appearance of one or more new lesions and/or unequivocal progression of existing non-target lesions (1)  |
| (1) Although a clear progression of non-target lesions only is exceptional, in such circumstances, the opinion of the treating physician should prevail and the progression status should be confirmed later on by follow-up imaging. |  |

**Evaluation of Best Overall Response:** The best overall response recorded from the start of the treatment until disease progression | recurrence (taking as reference for PD the smallest measurements recorded since the treatment started). In general, the participant’s best response assignment will depend on the achievement of both measurement and confirmation criteria.

| Target Lesions | Non-Target Lesions       | Evaluation of Non-Target Lesions | Overall Response |
|----------------|--------------------------|----------------------------------|------------------|
| CR             | CR                       | No                               | CR               |
| CR             | Incomplete Response   SD | No                               | PR               |
| PR             | Non-PD                   | No                               | PR               |
| SD             | Non-PD                   | No                               | SD               |
| PD             | Any                      | Yes or No                        | PD               |
| Any            | PD                       | Yes or No                        | PD               |
| Any            | Any                      | Yes                              | PD               |

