#### **Treatment Period:**

Vorinostat will be administered orally once daily continuously at 400 mg. Each treatment cycle will consist of 4 weeks of daily treatment.

Study visits will be conducted on weeks 2 and 4 ( $\pm 1$  day) for the first cycle, then for the second cycle on week 5 and 7, ( $\pm 1$  day); then from week 9 on, every four weeks ( $\pm 1$  day) thereafter for the remainder of the study. Patient medical histories, physical examinations, laboratory tests, assessments of compliance with study medication and recording of adverse events will be conducted during study visits. Further blood may be drawn for research correlatives. For patients that have been on study longer than 2 years, office visits can be done every 12 weeks ( $\pm 7$  days), with medical history, concurrent meds, physical exam, vital signs, weight, performance status, and adverse events evaluation done also at that time. For patients that have been on study longer than 2 years, hematology labs and serum chemistry can be done every 6 weeks ( $\pm 7$  days).

The severity duration and relationship to vorinostat will be determined for each adverse experience (AE) ([Section 11](#)).

Blood will be drawn on days 1 prior to first drug intake, and on days 7 (+- 1 day) and 28 (+- 1 day), prior to drug intake, to assess for correlative studies.

Patients will have radiological tumor assessment by computed tomography (CT) scan (or magnetic resonance imaging - MRI) on days -14 to -1 (prior to the start of vorinostat) and day 56 ( $\pm 3$  days). They will be followed with CT scans or MRI every 2 cycles / 8 weeks ( $\pm 1$  week) thereafter. Patients may receive scans every 3 cycles/12 weeks ( $\pm 1$  week) after completing 6 months of treatment on study. Patients that have been on study longer than 2 years can have tumor measurements (CT scans or MRI) done every 24 weeks ( $\pm 10$  days).

Predicated on obtaining funding, additional scans (optional) will be performed. These will include PET/CT scans prior to treatment, Day 28 ( $\pm 3$  days), and Day 56 ( $\pm 3$  days). An additional CT scan or MRI will also be performed on Day 28 ( $\pm 3$  days) for comparison purposes. The Day 28 CT/MRI and the PET/CT scans will be optional studies- due to financial issues (funding).

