## 5. TREATMENT PLAN

### 5.1 Vorinostat Administration

Treatment will be administered on an outpatient basis. Reported adverse events and potential risks are described in [Section 7](#). Appropriate dose modifications for vorinostat are described in [Section 6](#). No investigational or commercial agents or therapies other than those described below may be administered with the intent to treat the patient's malignancy.

On Day 1 of the first cycle of vorinostat will be initiated on a continuous daily oral regimen at 400mg PO. The dose may be reduced for individual patients in subsequent cycles depending on toxicity (See [Section 6.2.2](#)). Each treatment cycle will consist of 28 days of therapy.

Vorinostat can be taken with food. Patients need to swallow each capsule whole with a full glass of water. Capsules should not be chewed or opened. If a capsule is broken and the powder of the capsules gets on skin, patients should be instructed to wash the exposed area with copious amounts of water and to inform investigator or nurse of the fact.

Patients are required to record their daily dose in a "pills diary". Missed/ skipped pills or vomited doses should not be re-taken. Patients should be instructed to record those pills as missed doses in the diary and to inform investigator or nurse if that happens.

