## **6. DOSING DELAYS/DOSE MODIFICATIONS**

### **6.1 Retreatment Criteria**

Prior to administration of each new cycle following cycle one, patients must have recovered the following organ function:

- absolute neutrophil count  $\geq 1.5 \times 10^9/L$
- platelets  $\geq 100 \times 10^9/L$
- creatinine  $\leq 1.5 \times$  upper limit of normal (ULN)
- other drug related toxicity must have recovered to  $\leq$  grade 1 (excluding alopecia, controllable hypertension, leukopenia and lymphopenia)
- total bilirubin WNL
- AST(SGOT)/ALT(SGPT)  $\leq 2.5 \times$  ULN

Patients not fulfilling these criteria should have treatment delayed by 1 week to allow for recovery of organ function. Patients who cannot be retreated within 3 weeks (21 days) of the end of the previous cycle should be removed from study, unless they are deriving benefit. In the later case, a discussion with the PI and/or CTEP senior investigator will ensue.

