| Tumor measurements p               | X c             | Tumor measurements are repeated every 8 weeks ( $\pm$ 1 week) for the first 6 cycles. After 6 months on study, can be performed every 12 weeks ( $\pm$ 1 week). Documentation (radiologic) must be provided for patients removed from study for progressive disease. Objective responses should be confirmed within 4 weeks. |                |      |                |                |      |                |      |                |          |                | X h |
| Archival tumor tissue collected               | X b             |  |                |      |                |                |      |                |      |                |          |                |                |
| Blood for correlative studies j, m |                            | X  |                |      | X              |                |      |                |      |                |          |                |                |

|   |                |  |  |  |                |  |  |  |                |  |  |  |  |  |
|---|----------------|--|--|--|----------------|--|--|--|----------------|--|--|--|--|--|
| PET/CT L   | X c |  |  |  | X i |  |  |  | X i |  |  |  |  |  |

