
## 10. MEASUREMENT OF EFFECT

For the purposes of this study, patients should be re-evaluated for response every 8\_ weeks. Patients may receive scans every 3 cycles/12 weeks ( $\pm$  1 week) after completing 6 months of treatment on study. Patients that have been on study longer than 2 years can have tumor measurements (CT scans or MRI) done every 24 weeks ( $\pm$ 10 days). In addition to a baseline scan, confirmatory scans should also be obtained 4 (not less than 4) weeks following initial documentation of objective response.

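### Tumour assessments are timed by the calendar in some places and by treatment cycle in others, with no rule for a delayed cycle; this could bias 6-month PFS and stable disease duration upward

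*Combined protocol and SAP*

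**What the plan says.** Three kinds of timing rule coexist in the current text.

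- **Calendar time.** The Schema (Treatment Period) puts the first on-treatment scan at day 56 ±3 days. The tumour measurement row of the Study Calendar (Section 9) says "Tumor measurements are repeated every 8 weeks", with a ±1 week window, and allows 12-week spacing after 6 months. Section 10 also sets re-evaluation every 8 weeks. After 2 years, all three allow 24 weeks ±10 days.
- **Cycles and weeks treated as equal.** The Schema says "They will be followed with CT scans or MRI every 2 cycles / 8 weeks" for scans after day 56, and Section 10 says "Patients may receive scans every 3 cycles/12 weeks" once 6 months of treatment are complete. The Schema has a matching 3-cycle provision. The Study Calendar limits its 8-week spacing to the first six cycles but starts the wider spacing at six months.
- **Cycle only.** Appendix C (2.2 Image Data Analysis) says "measurements obtained following chemotherapy cycles will be obtained on scans performed within 1-3 days of the next cycle of treatment". Appendix C, 2.1, applies its RECIST assessment to every CT scan in the trial.

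Section 5.1 sets the cycle length: "Each treatment cycle will consist of 28 days of therapy". Section 6.1 delays a new cycle in 1-week steps until toxicity recovers, with this limit: "Patients who cannot be retreated within 3 weeks (21 days) of the end of the previous cycle should be removed from study". Patients deriving benefit are excepted after discussion. Section 6.2.1 repeats the 21-day limit for holds within a cycle. No section says which clock governs imaging when a cycle starts late.

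**The concern.** Under the cycle clock, the time of a scan depends on toxicity: patients whose cycles are delayed are assessed later than the rest. Apart from deaths counted in PFS, the PFS and stable disease duration endpoints (Sections 10.1.5 and 10.1.6) run from the start of treatment to an event that only a scan can date. Later scans can therefore lengthen them in the patients receiving less drug. Sites that follow different sections would also produce different schedules within a trial of at most 29 response-evaluable patients.

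The 6-month point is the most exposed. Section 12.4 gives the 6-month event-free rate as an example summary. Section 2.1 calls stable disease of 6 months or more a possibly relevant exploratory endpoint, and Section 1.3 and Appendix I use stable disease beyond 6 months as a response category. The nominal week 24 scan falls about 2 weeks before that landmark.

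**Working it through.** **The plan's own figures.** The documents give no figure for scan timing or for expected PFS. The only design figures are those of Section 12.1.1: stop if 0 of 12 respond, and call the drug promising if at least 3 of 29 respond.

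- Early termination at a 5% response rate: 0.95^12 = 0.540.
- P(promising) = Σ over x = 1 to 12 of b(x; 12, p) × P[Bin(17, p) ≥ max(0, 3 − x)]. This gives 0.148 at p = 0.05 and 0.9005 at p = 0.20.

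The stated 0.15, 0.90 and 0.540 reproduce. The formula uses response counts and contains no scan-time term.

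**Scan dates under each clock.** Inputs are 28-day cycles (Section 5.1), delays of 1 to 3 weeks (Section 6.1), and scans just before cycles 3, 5 and 7 and then every 3 cycles (Schema with Appendix C).

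| Case | Scan weeks |
|---|---|
| Calendar, or no delay | 8, 16, 24, 36, 48 |
| One 3-week delay before the first scan, cycle clock | 11, 19, 27, 39, 51 |
| 3-week delay before every next cycle, cycle clock | 14, 28, 42, 63, 84 |

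For one 3-week delay the first scan falls at 28 + 21 + 28 = 77 days, or 11 weeks, which is outside ±1 week. For one 1-week delay it falls at 56 + 7 = day 63. That is inside ±1 week but outside day 56 ±3, whose upper limit is day 59.

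The Study Calendar's two switch points also differ: six undelayed cycles are 6 × 4 = 24 weeks, while six months is about 26.1 weeks.

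**Effect at 6 months (26.09 weeks).** A progression is counted by 6 months only if it precedes the last scan before week 26.09. The observed event-free rate is therefore S(time of that scan). Assume exponential progression with a true median of 9 months (39.1 weeks), so S(t) = 0.5^(t/39.1).

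- True rate: S(26.09) = 0.63.
- Calendar clock, last scan at week 24: 0.654.
- One 3-week delay in every patient, last scan at week 19: 0.714.
- One 3-week delay in 25% of patients: 0.75 × 0.654 + 0.25 × 0.714 = 0.669, about 0.67.
- Maximum delay at every cycle in every patient, last scan at week 14: 0.780. In 25% of patients: about 0.69.

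The true median is an assumption, so the range for one 3-week delay in every patient is:

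| Assumed true median (months) | Calendar | All delayed once | Difference |
|---|---|---|---|
| 4 | 0.384 | 0.468 | 0.084 |
| 6 | 0.528 | 0.603 | 0.075 |
| 9 | 0.654 | 0.714 | 0.060 |
| 12 | 0.726 | 0.776 | 0.050 |

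With a quarter of patients delayed, the difference is a quarter of this, about 0.01 to 0.02.

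**Effect on mean detection time.** Simulation of 400,000 patients per assumed median (4, 6, 9, 12 months) gives a mean lag from true progression to detection of 5.08, 5.29, 5.48 and 5.59 weeks on the calendar clock. After one 3-week delay the lags are 5.58, 5.62, 5.69 and 5.74 weeks, so the shift is 0.50, 0.33, 0.21 and 0.15 weeks. It is small because some events are found sooner: progression between weeks 8 and 11 is seen at week 11 instead of week 16. The observed median can move either way. It goes from 36 to 27 weeks at a true median of 6 months, and from 48 to 51 weeks at 9 months.

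**The case against.** Most of the operative text is in calendar time. Even the paired phrases carry tolerances in weeks, so a sensible site could read cycles as shorthand for the stated weeks. Appendix C places a scan near the next cycle but sets no interval, and Section 2.3 cites it as guidance for the optional PET/CT data. The documents give no frequency of delays. With 29 patients, the 90% half-width for a rate near 0.65 is about 1.645 × √(0.65 × 0.35 / 29) = 0.15. That is far larger than a shift of 0.01 to 0.02.

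Much of this stands, and it limits the size of the point. It does not remove it: Appendix C, 2.1, extends that appendix to all CT scans, and no section ranks the clocks.

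A reader might also compute much longer gaps: 2 × (28 + 21) = 98 days instead of 8 weeks, and 3 × (28 + 21) = 147 days instead of 12. These require the maximum delay before every next cycle and the Appendix C rule. Applied to the first scan, they also override the explicit day 56 ±3 rule. Two cycles counted from day 1 without the next-cycle rule take at most 28 + 21 + 28 = 77 days under the 21-day limit. The 98- and 147-day figures are bounds under that limit, not expectations.

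**Conclusion.** The passages conflict once a cycle is delayed, and they need one governing clock. Where a site uses the cycle clock, patients with toxicity delays can be scanned late. This could bias PFS and stable disease duration upward, mainly at 6 months: by about 0.01 to 0.02 if a quarter of patients have one 3-week delay, and by 0.05 to 0.08 if all do. These sizes assume exponential progression with true medians of 4 to 12 months, full use of the cycle clock in delayed patients, and a delay occurring before the first scan.

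Three stronger conclusions might be inferred, and the documents do not support them.

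- That delayed patients are scanned late and their PFS is inflated as a matter of fact. This depends on which section a site follows, and after one delay the mean shift is under 1 week.
- That time to response is inflated in the drug's favour. It applies to responders only (Section 10.2.1), and a later response date does not flatter the drug.
- That the go/no-go decision is compromised. The Simon design's operating characteristics are unchanged, the trial has one arm, and the affected endpoints are secondary or exploratory.

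The change is worth making because it is cheap and removes a dependence of outcome measurement on toxicity.

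**What to change.** Reconcile the Schema, the Study Calendar, Section 10 and Appendix C, 2.2. State once that endpoint imaging is timed in calendar weeks from day 1, regardless of dose holds or cycle delays, with the spacings and windows already permitted. Specifically:

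- Remove the cycle wording, or make it subordinate to the weeks, in the Schema (2-cycle and 3-cycle phrases) and in Section 10 (3-cycle phrase only).
- Remove or subordinate the next-cycle rule in Appendix C, 2.2.
- Use one switch point in the Study Calendar in place of both six cycles and six months.

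This concerns outcome measurement only. The dosing, hold and delay rules of Section 6 are not affected.

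The cost is a short clarification with no new scan types. The downside is that a delayed patient may be scanned mid-cycle. Section 8 shows that patients have already been treated, and new wording cannot correct their scans. For them, a listing of actual scan dates against cycle delays, with a sensitivity analysis of PFS and stable disease duration, would show whether the issue arose.
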